#### 4.12 Determination of Sample Size

The sample size is calculated based on the following assumptions:

- A 40% response rate for the active Viaskin® Peanut 250 µg group and 10% response rate for the placebo group, both estimated under “Missing=failure” method (based on a maximum drop-out rate of 15%) in the overall population;
- A lower bound of the 95% CI of the difference between active treatment and placebo response rates  $\geq 15\%$  in the overall population and  $>0\%$  in each screening ED stratum;
- A 60% response rate for the active Viaskin® Peanut 250 µg group and 10% response rate for the placebo group in screening ED Stratum 1, both estimated under “Missing=failure” method (based on a maximum drop-out rate of 15%);
- A 30% response rate for the active Viaskin® Peanut 250 µg group and 10% response rate for the placebo group in screening ED Stratum 2, both estimated under “Missing=failure” method (based on a maximum drop-out rate of 15%);
- The following expected distribution of the screening ED strata:
  - o 1/3 of children having a screening ED from 1 mg to 10 mg;

- o 2/3 of children having a screening ED from 30 mg to 300 mg.
- A ratio 2:1 to maximize the number of subjects treated in the active Viaskin® Peanut 250 µg group.

Therefore, the overall sample size calculated is approximately 330 subjects evaluable for the primary efficacy endpoint in the analysis (220 subjects in the active Viaskin® Peanut 250 µg group and 110 subjects in the placebo group). Hence, according to the expected distribution of the screening ED strata, approximately 110 children having a screening ED from 1 mg to 10 mg and 220 children having a screening ED from 30 mg to 300 mg should be randomized.

This number of subjects leads to a power of >90% in the overall population, >99% in the Stratum 1 and >95% in the Stratum 2.

This is summarized in the following Table.

### Summary of Sample Size Calculations

Population	Lower bound of the 95% CI of the difference	Power	Sample size (N=N1+N2) Expected Response Rate		
			Viaskin ® Peanut 250 µg	Placebo	Total
Overall population	≥15%	90%	N1=220 40%	N2=110 10%	N=330
Screening ED Stratum 1	>0%	99%	N1=73 60%	N2=37 10%	N=110
Screening ED Stratum 2	>0%	95%	N1=146 30%	N2=74 10%	N=220

Abbreviations: CI = Confidence interval; ED = Eliciting dose; N = Number of subjects.

Among the 330 subjects randomized, a minimum of 25 subjects should be randomized for each of the following ages: 4 years, 5 years and 11 years, respectively. Additionally, a minimum number of 75 children of either 4 or 5 years of age should be randomized.

The distribution per ED stratum should lead to approximately 110 subjects with a screening ED from 1 mg to 10 mg and approximately 220 subjects with a screening ED from 30 mg to 300 mg, provided that the same distribution as obtained in the Phase IIb VIPES study is reproduced. If this expected distribution is not fully respected during the recruitment in the PEPITES study, a minimum of 50 subjects would need to be included in Stratum 1 in order to guarantee a power of >95% in this stratum and at least 220 subjects would need to be included in Stratum 2 in order to guarantee a power of >95% in this stratum.

From experience, the screen failure rate could be as high as 30%; hence, up to 470 peanut allergic subjects might need to be screened.

#### 4.13 Changes in the Conduct of the Study or Analysis planned in protocol

- To handle cases of randomization stratum error (i.e. the stratum recorded in the IWRS differs from the actual one documented in the eCRF), screening ED

subgroups were considered for secondary analyses using actual screening ED values (i.e. subjects will be considered in the screening ED subgroup corresponding to their actual screening ED value).

- Following FDA comment,, the primary measure of treatment effect will be the difference in response rates between active and placebo treatment groups. The primary analysis will apply a Wald test at a 2-sided 5% significance level to evaluate a null hypothesis of no difference, and a 2-sided Newcombe 95% confidence interval (CI) for the difference in response rates will be calculated. The clinical relevance criterion for the primary analysis will be defined by a  $\geq 15\%$  lower confidence bound of the Newcombe CI, and this condition will determine whether the primary objective has been successfully met, as recommended by FDA.

The Wald test p-value will be calculated using the SAS® GENMOD procedure, with DIST=binomial and LINK=identity option of the MODEL statement.

The 2-sided Wilson 95% CIs of individual response rate will be presented by treatment group using the SAS® FREQ procedure.

- Per protocol, descriptions by age group (4-5, 6-11 years of age) are planned for treatment response rate. Descriptions by age group (4-5, 6-11 years of age) will also be provided for Cumulative reactive dose, Percentage of subjects responsive/unresponsive to a cumulative dose of  $\geq 1,444$  mg peanut protein and Percentage of subjects unresponsive to the highest cumulative dose of peanut protein.
- IgE and IgG4 values at M12 were planned to be analyzed using an ANCOVA model. IgE and IgG4 results will be analyzed using a repeated-measures ANCOVA model taking into account all time points up to M12 to compare the mean absolute change from Baseline in the Viaskin 250  $\mu$ g group vs Placebo.
- SPT description will be performed in the overall population, as well as for each screening ED subgroup.
- FAQLQ questionnaires (Child form and Parent form) will be analyzed using a global score (as described in the protocol) and, additionally, by domain and by item.
- The region effect will be explored for primary efficacy endpoint only.  
As sensitivity analysis of primary analysis:
  - On the ITT population, using missing=failure imputation for missing data, Cochran-Mantel-Haenszel (CMH) method with region as stratification variable to compute a Newcombe 95% CI for the region-adjusted difference in response rates.

Response rates by treatment groups and treatment effect will also be provided descriptively, as exploratory analysis, for each region.

Exploration of region effect for secondary analyses was removed.

- The proportion of days with mild, moderate or severe TEAE occurring during the exposure period will be studied. This additional safety description will be performed on the Safety population.
- Description of risk-taking behavior will be performed on the Safety population (instead of the ITT population).
- The randomization was not stratified by site.
- Methodologies to impute missing data at Month 12 for primary analysis and secondary analysis were revised to address the cases where:
  - ⌞ the DBPCFC is stopped without the objective symptoms leading to ending the DBPCFC (stopping rules) OR
  - ⌞ the subject took the 2,000mg dose without any objective symptom leading to ending the DBPCFC.

## 6 APPENDICES

### 6.1 Appendix 1: Major Protocol deviations

This table provides a sample of attitude taken regarding inclusion or exclusion of subjects with major protocol deviations in the analysis sets. Categories of major protocol deviations will be discussed and finalised during blind data review meetings.

Major Protocol Deviation	Action to be Taken For Analysis
Subject did not take any study medication	Exclude from all population except ITT
Subject took incorrect study medication	Analyze 'As-randomized' for ITT Analysis. Analyze 'As-treated' for Safety Analysis. Exclude from PP population
Subject failed to meet study inclusion criteria but was entered into the study.	Exclude from PP population if it could have an impact of the Primary efficacy criteria
Subject met study exclusion criteria but was entered into the study.	Exclude from PP population if it could have an impact of the Primary efficacy criteria
Subject met study withdrawal criteria but was not withdrawn.	Exclude from PP population if it could have an impact of the Primary efficacy criteria
Subject non-compliant with study medication regimen (<80% compliant)	Exclude from PP population
Subject non-compliant with study assessment schedule:	
Subjects who do not perform the DBPCFC at 12 months	Exclude from PP population and Full analysis sets.
Visit not within a pre-specified window after baseline visit.	Exclude from PP population if it could have an impact of the Primary efficacy criteria
Subject took prohibited concomitant medication	Exclude from PP population if it could have an impact of the Primary efficacy criteria
Subject is stratified incorrectly	'Actual stratum' will be used to define screening ED subgroup

## 6.2 Appendix 2: SAS® Code lines

The SAS code lines provided in Appendices 2 are provisional and can be used as a guidance. Further updates to this code lines might be necessary.

### Appendix 2.1: Statistical analysis methods and procedures used for the analysis of the primary efficacy endpoint.

The following notations in lower case will be used in the SAS® code lines provided below:

resp	=	Binary variable for treatment response
trt	=	Binary variable for study treatment
sed	=	Binary variable for screening ED stratum
reg	=	Region

Calculating the response rates in each two group and getting the corresponding 2-sided 95% Wilson CIs.

Calculating the difference between active and placebo response rates and getting the corresponding 2-sided 95% Newcombe CI.

---

```
PROC FREQ;
TABLES RESP /ALPHA=0.05 BINOMIAL(WILSON);
BY TRT ;
run;
PROC FREQ;
TABLES trt*resp/ ALPHA=0.025 RISKDIFF(SUP MARGIN=0.15
METHOD=NEWCOMBE);
RUN;
```

---

- Calculating the p-value of the Wald test for the difference between active treatment and placebo response rates

---

```
PROC GENMOD;
CLASS trt;
MODEL resp = trt / DIST=BIN LINK=IDENTITY;
RUN;
```

---

Sensitivity analyses:

- Cochran-Mantel-Haenszel (CMH) method with Screening ED randomization stratum (Screening ED > 10 mg/Screening ED ≤ 10 mg) as stratification variable to compute a Newcombe 95% CI for the strata-adjusted difference in response rates [5].

---

```
%stratCI (data=, treatment= trt, strata=sed, response= resp, level=0.05);
```

---

- Cochran-Mantel-Haenszel (CMH) method with region as stratification variable to compute a Newcombe 95% CI for the region-adjusted difference in response rates [5].

---

```
%stratCI (data=, treatment= trt, strata=reg, response= resp, level=0.05);
```

---

## Appendix 2.2: Strategy of analysis of the primary efficacy endpoint using multiple imputation of missing data

The following notations in minor case will be used in the SAS® code lines provided below:

resp	=	Binary Variable for treatment response
trt	=	Binary variable for study treatment
sed	=	Binary variable for screening ED stratum

The following steps will be performed along with the specified SAS code [3]:

- **Step 1:** Running a Multiple imputation of the response rate on 1000 datasets using the SAS® MI procedure. The seed used will be specified in the table output and in the table footnote (process will be rerun using an alternative seed to check for the stability of the results – corresponding results will not be provided in the table outputs but archived as a statistical appendix). A monotone logistic model on the Baseline screening ED stratum will be used to perform the imputations. The multiple imputations will be performed by keeping in the procedure placebo subjects with non-missing data along with any subject with missing data. Thus the probability distribution that imputes the missing response will rely on placebo subjects with a response and so the missing data would mimic placebo response

---

```
PROC MI NIMPUTE=1000 OUT=<imputed data> SEED=<seed
number=223218> ;
CLASS resp sed;
MONOTONE LOGISTIC (resp=sed/DETAILS) ;
VAR sed resp ; RUN ;
```

---

- **Step 2:** Adding to the imputed dataset with 1000 replications for each subject (identified by the variable `_IMPUTATION_`), a thousand times the subjects under the active treatment that had no missing value for treatment response (subjects that were excluded from the preceding MI procedure)
- **Step 3:** Calculation of the rate of responders for each treatment group for each imputed dataset using SAS® FREQ procedure and creating a dataset containing estimated response rate and their standard error in each treatment group.

---

```
PROC FREQ DATA=<imputed data as obtained from step 2>;
BY _IMPUTATION_ trt ;
TABLES resp / BINOMIAL(WILSON);
ODS OUTPUT BINOMIALPROP=< response rate> ;
DATA <response rate and SE>;
MERGE < response rate> (WHERE=(LABEL1="Proportion")
KEEP=_IMPUTATION_ trt NVALUE1 LABEL1
RENAME=(NVALUE1=p))
<exact response rate> (WHERE=(LABEL1="ASE")
KEEP=_IMPUTATION_ trt NVALUE1 LABEL1
RENAME=(NVALUE1=se));
BY _IMPUTATION_ trt ;
```

---

---

```
RUN;
PROC SORT; BY trt _IMPUTATION_;
RUN;
```

---

Note:

p = Variable for response rate  
se = Variable for standard error for response rate

---

- **Step 4:** Calculation of the combined estimate of the response rate in each treatment group using dataset created in step 3.

---

```
DATA <response rate difference and SE>;
MERGE <response rate and SE> (WHERE=(trt=2) RENAME=(p=P2 se=SE1))
    <response rate and SE> (WHERE=(trt=1) RENAME=(p=P1 se=SE2));
    BY _IMPUTATION_;
    RUN;
PROC MIANALYZE DATA=<response rate and SE from step 3>;
MODELEFFECTS p1 p2;
STDERR se1 se2;
ODS OUTPUT PARAMETERESTIMATES=<combined estimates of response rate>;
RUN;
```

---

- **Step 5:** Calculation of the Wilson confidence interval of the combined estimate of the response rate in each treatment group using dataset created in step 3.
- Calculation of the combined estimate of the difference in response rate between the two treatment groups and the Newcombe confidence interval using dataset created in step 3.

---

```
DATA <combined estimates of response rate Wilson IC trt1> (WHERE=(parm=p1));
SET <combined estimates of response rate>;
quartile_norm=quantile("normal",0.975);
Wilson=1
L1= (Estimate+quartile_norm*quartile_norm/(2*n1)-quartile_norm*sqrt((Estimate*(1-
Estimate)+(quartile_norm*quartile_norm)/(4* n1))/ n1))
/(1+(quartile_norm*quartile_norm)/ n1);
U1=(Estimate+quartile_norm*quartile_norm/(2*n1)+quartile_norm*sqrt((Estimate*(1-
Estimate)+(quartile_norm*quartile_norm)/(4* n1))/ n1))
/(1+(quartile_norm*quartile_norm)/ n1);
RUN;
```

```
DATA <combined estimates of response rate Wilson IC trt2> (WHERE=(parm=p2));
SET <combined estimates of response rate>;
quartile_norm=quantile("normal",0.975);
Wilson=1
L2= (Estimate+quartile_norm*quartile_norm/(2*n2)-quartile_norm*sqrt((Estimate*(1-
Estimate)+(quartile_norm*quartile_norm)/(4* n2))/ n2))
/(1+(quartile_norm*quartile_norm)/ n2);
U2= (Estimate+quartile_norm*quartile_norm/(2* n2)+quartile_norm*sqrt((Estimate*(1-
Estimate)+(quartile_norm*quartile_norm)/(4* n2))/ n2))
/(1+(quartile_norm*quartile_norm)/ n2);
RUN;
```

---

---

```
DATA <combined estimates of difference in response rate Newcombe IC>
MERGE < combined estimates of response rate Wilson IC trt1 > < combined estimates of
response rate Wilson IC trt2 >
by Wilson;
p_d =p1-p2;
dL=(p1-p2)-sqrt((p1-L1)*(p1-L1)+(U2-p2)*(U2-p2));
dU=(p1-p2)+sqrt((U1-p1)*(U1-p1)+(p2-L2)*(P2-L2));
RUN;
```

---

Note:

p1	=	Variable for estimated response rate
se1	=	Variable for standard error of estimated response rate
p2	=	Variable for estimated response rate
se2	=	Variable for standard error of estimated response rate
n1	=	N for treatment 1
n2	=	N for treatment 2
p_d	=	Variable name for estimated difference in response rate between treatment
dL	=	Variable for the lower bound of Newcombe confidence interval
dU	=	Variable for the upper bound of Newcombe confidence interval

### **Appendix 2.3: Statistical analysis methods and procedures used for the analysis of the cumulative reactive dose of peanut protein at month 12.**

The following notations in minor case will be used in the SAS® code lines provided below:

Crd0(12) = Variable for Peanut protein cumulative reactive dose at Baseline (M12)
 
trt = Binary variable for study treatment

---

- The peanut protein cumulative reactive dose in each treatment group at M12 will be compared using an analysis of covariance (ANCOVA) model. The ANCOVA model will include the treatment group, adjusted for the Baseline value.

```
PROC MIXED ;  
CLASS trt;  
MODEL crd12=trt crd0 / DDFM=KR ;  
LSMEANS trt / CL DIFF OM ;  
ODS OUTPUT LSMEANS=<least square means>  
DIFFS=<least square means differences> ;  
RUN ;
```

#### **Appendix 2.4: Statistical analysis methods and procedures used for the analysis over time of peanut-specific IgE and IgG4.**

The following notations in minor case will be used in the SAS® code lines provided below:

trt	=	Binary variable for study treatment
x0	=	Peanut specific IgE (IgG4) at Baseline
visit	=	Visit variable 1=M3, 2=M6, 3=M12
chx	=	Absolute change in Peanut specific IgE (IgG4 or skin prick test value) at: M3 (for visit=1) M6 (for visit=2) M12 (for visit=3)
sed	=	Binary variable for screening ED subgroup
Id	=	Subject Identification

- The analysis of peanut-specific IgE and IgG4 over time will be performed using a repeated-measure analysis of covariance (ANCOVA). The ANCOVA model will include the treatment group, adjusted for the Baseline value and the screening ED subgroup. The input data set will have one observation by visit (up to 3 by subject).

---

```
PROC MIXED ;  
CLASS visit id trt sed;  
MODEL chx=trt x0 sed trt*visit visit;  
REPEATED visit / type=UN SUBJECT=id;  
LSMEANS visit trt visit * trt / PDIFF=ALL CL;  
RUN
```

---

### 6.3 Appendix 3: Common Terminology Criteria for Adverse Events (CTCAE) grades

Haematology	G1	G2	G3	G4
Red blood cells (x10e12 /L)	No grading according to CTCAE			
Hematocrit (V/V)	No grading according to CTCAE			
Hemoglobin (g/L) - low	[100;LLN[	[80;100[	<80	
Hemoglobin (g/L) - high	]ULN;ULN+20]	]ULN+20;ULN+40]	>ULN+40	
Platelets (x10e9 /L) - low	[75;LLN [	[50;75[	[25;50[	<25
Leucocytes (x10e9 /L) - low	[3;LLN[	[2;3[	[1;2[	<1
Neutrophils (x10e9 /L) - low	[1.5;LLN[	[1;1.5[	[0.5;1[	<0.5
Eosinophils (x10e9 /L)	No grading according to CTCAE			
Basophils (x10e9 /L)	No grading according to CTCAE			
Lymphocytes (x10e9 /L) - low	[0.8;LLN[	[0.5;0.8[	[0.2;0.5[	<0.2
Monocytes (x10e9 /L)	No grading according to CTCAE			

Biochemistry	G1	G2	G3	G4
BUN/urea (mmol/L)	No grading according to CTCAE			
Total protein (g/L)	No grading according to CTCAE			
Total bilirubin (µmol/L) – high	ULN; ULN*1.5]	]ULN*1.5; ULN*3]	]ULN*3;ULN*10]	>ULN*10
AST (U/L) - high	]ULN; ULN*3]	]ULN*3; ULN*5]	]ULN*5;ULN*20]	>ULN*20
ALT (U/L) - high	]ULN; ULN*3]	]ULN*3; ULN*5]	]ULN*5;ULN*20]	>ULN*20
Creatinine (µmol/L) - high	]ULN; ULN*1.5]	]ULN*1.5; ULN*3]	]ULN*3;ULN*6]	>ULN*6

### 6.4 Appendix 4: List of Post-Text Tables, figures, listings, and Supportive SAS output appendices

Will be provided in a separate document.

## **6.5 Appendix 5: Methodology of identification of systemic allergic adverse events**

This methodology will be based on the MedDRA SMQ “Anaphylactic reaction” (MedDRA version in use at the time of study results analysis) as described in the “Introductory Guide for Standardised MedDRA Queries (SMQs) Version 20.0.

The retrieval will be performed in the SMQ anaphylactic reaction using an algorithmic approach which combines a number of anaphylactic reaction symptoms in order to increase specificity. A case must include either:

- A narrow term or a term from Category A;
- A term from Category B - (Upper Airway/Respiratory) AND a term from Category C - (Angioedema/Urticaria/Pruritus/Flush);
- A term from Category D - (Cardiovascular/Hypotension) AND [a term from Category B - (Upper Airway/Respiratory) OR a term from Category C - (Angioedema/Urticaria/ Pruritus/Flush)]

The events will be considered as concomitant for the algorithm output if they appear on the same day +/- 1 day.

- Related AESI will be determined if at least on term of any association in the algorithm is “related”.
- Unrelated AESI will be determined if all terms of any association in the algorithm are not “related”.
- Where dates are missing or partially missing, adverse events are not considered for possible association.”

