##### **Analyses of other efficacy, safety and exploratory criteria:**

No imputation will be performed for other efficacy, safety and exploratory criteria (observed data will be used). Partial or missing safety data will be imputed according to the most conservative approach. Adverse events with missing or incomplete onset date will be considered as TEAEs unless there is evidence that the event occurred prior to the treatment period. Treatment-emergent AEs with missing relationship to the study drug will be considered as drug-related and TEAEs with missing severity will be considered as severe. Actual values will be presented in listings.

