##### Cumulative Reactive Dose (CRD)

The cumulative reactive dose of peanut (CRD) will be calculated as follow

CCI

CONFIDENTIAL

Project Document Version No. 3.0

Project Document Effective Date: 04-Oct-2017

Page 32 of 79

- If the ED reported by the investigator in the eCRF is missing, then the CRD is missing
- If the ED reported by the investigator in the eCRF is not missing then the CRD is calculated as the sum of all doses given, including also the repeated and partial doses; doses greater than the ED are not included in the calculation. Example:  
For a particular patient if the set of recorded doses is {1, 3, 10, 30, 100, 300, 300, 1000}, and recorded ED = 300mg, then  $CRD = 1 + 3 + 10 + 30 + 100 + 2 \times 300 = 744mg$ .

No imputation will be performed for other efficacy, safety and exploratory parameters. In those instances observed data will be used, excepted for safety data where partial or missing data will be imputed according to the most conservative approach (See [Section 4.9.1: Adverse Events](#)).

Actual values will be presented in listings.

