#### 4.9.1 Adverse Events

Treatment-emergent AEs will be defined as any AEs, regardless of relationship to study drug reported during or after the initial Viaskin® patch application, i.e.:

- New event, or
- Condition already present that worsens in either severity or relationship to study drug following exposure to Viaskin® patches.

AEs occurring after the end of the study (Visit 11 or Visit 12) will be recorded only if the investigator considers that there is a causal relationship with the study drug and as such, will be considered also as TEAEs.

Pre-treatment emergent AE will be defined as an AE that begins before the first administration of study drug and that does not worsen in severity after the first administration of study drug. During the screening period (from the ICF signature to Day-1), only SAEs are recorded in the database (AEs are only documented in the source documents).

Where dates are missing or partially missing, adverse events will be assumed to be treatment-emergent, unless there is clear evidence (through comparison of partial dates) to suggest that the adverse event started prior to the first dose of study treatment.

More specifically:

- Start date of AE missing: Assumed to be date of first treatment dose.
- Start day and month of AE missing: Assumed to be date of first treatment dose (if same year for both dates), January 1st otherwise.
- Start day of AE missing: Assumed to be date of first treatment dose (if same month and year for both dates), first day of the month otherwise.
- End date for non-ongoing AE missing: Assumed to date of last treatment dose
- End day and month for non-ongoing AE missing: Assumed to be date of last treatment dose (if same year for both dates), December 31st otherwise.

- End day for non-ongoing AE missing: Assumed to be date of last treatment dose (if same month and year for both dates), last day of the month otherwise.

TEAEs with missing severity will be considered as “severe”; TEAEs with missing relationship to the study drug will be considered as “drug-related”.

TEAEs reported as related, probably related, or possibly related to the study drug will be considered as related to IP.

Viaskin Peanut-induced Local TEAEs are defined as TEAEs considered as related to IP with a High Level Term equal to “Application and instillation site reactions” and will be flagged in the analysis datasets.

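### SAP Appendix 5 leaves adverse events with incomplete dates out of the two-term pairing for systemic allergic reactions; the exception is unexplained, and the number of subjects with any case or a related case can only fall

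*SAP*

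**What the plan says.** SAP 4.9.5 identifies the systemic allergic adverse events of special interest with the algorithm in Appendix 5 and reports them by subject and by case, with related and unrelated cases shown separately.

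Appendix 5 gives two routes to a case.

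- **Single term:** "A narrow term or a term from Category A".
- **Two terms:** for example "A term from Category B - (Upper Airway/Respiratory) AND a term from Category C - (Angioedema/Urticaria/Pruritus/Flush"), or a cardiovascular term (Category D) with a term from B or C. Timing is set by this rule: "The events will be considered as concomitant for the algorithm output if they appear on the same day +/- 1 day".

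Relatedness needs only one related component: "Related AESI will be determined if at least on term of any association in the algorithm is “related". The last bullet of the appendix then states: "Where dates are missing or partially missing, adverse events are not considered for possible association".

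Elsewhere the plan leans the other way on incomplete safety data. Protocol 8.2.2.4 says "Partial or missing safety data will be imputed according to the most conservative approach". SAP 4.8.1.2 makes the same exception to its no-imputation rule, "excepted for safety data where partial or missing data will be imputed according to the most conservative approach", and points to SAP 4.9.1. That section says "Where dates are missing or partially missing, adverse events will be assumed to be treatment-emergent" unless there is clear evidence otherwise, and gives rules for filling in start and end dates. Neither Appendix 5 nor the list of changes in SAP 4.13 explains why pairing is treated differently.

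**The concern.** Protocol 1.3 names systemic, severe or life-threatening allergic reaction as the primary safety concern for this class of treatment. Protocol 6.2.1.3.5 makes systemic IgE-mediated symptoms, at least possibly related to study drug, an event of special interest. The Appendix 5 algorithm decides which children enter those tables.

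If a child has an airway event and a skin event from the same reaction and one lacks a day, the pair cannot form, even when the other is fully dated in the same month. A missing day says nothing about whether the reaction was systemic. For a safety count, a rule that can remove cases but not add them errs in the less cautious direction.

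The bullet is also loosely specified. It says dates, not onset dates, so read literally an event with a full onset date and a partial end date is dropped too. It does not say whether it applies before or after the SAP 4.9.1 imputation. Two programmers could therefore count different cases, although SAP 4.1 requires independently programmed datasets to match.

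**Working it through.** The plan gives no figure on this point, so there is none to reproduce. The check has three parts.

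**1. What each passage governs.**

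| Place | Handling of incomplete dates | Question it answers |
|---|---|---|
| Protocol 8.2.2.4 | Most conservative approach, then applied to treatment emergence, relationship and severity | Is the event counted, and how? |
| SAP 4.8.1.2 | Same principle, refers to 4.9.1 | Same |
| SAP 4.9.1 | Event kept; start and end dates filled in | Is it treatment-emergent, and how long did it last? |
| SAP Appendix 5 | Event left out of pairing | Did two events occur together? |

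The first three share a principle that Appendix 5 does not follow. None of them sets a rule for concomitance.

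**2. Direction.** Taking events away cannot create a pair. To confirm this with relatedness included, every set of one to three events was enumerated: Categories A to D (A standing for any single-term case), days 0 to 2, related or not. Each set was compared with itself after removing every possible choice of partially dated B, C or D events, while single-term events still counted alone. This gave 19,124 comparisons of one child's status.

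| Status of the child | Gained | Lost |
|---|---|---|
| Any systemic allergic case | 0 | 4,872 |
| A related case | 0 | 5,292 |
| Unrelated case only | 1,293 | 873 |

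These are counts of configurations, not probabilities; they show direction only. An example of the third row is a child with an unrelated single-term event, an unrelated B event and a related C event on the same day. With full dates the B+C pair makes the child a related case. If B lacks its day, the pair is lost and only the unrelated single-term case remains. The child has been reclassified, not added.

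**3. Size.** Let q be the share of component events with an incomplete date. The documents give no value, so q is an assumption. A case resting on exactly two terms is lost if either is incomplete:

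loss = 2q − P(both incomplete)

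- Gaps fully correlated: P(both) = q, so loss = q.
- Gaps independent: P(both) = q², so loss = 2q − q² = 1 − (1 − q)².

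| q (assumed) | Correlated | Independent |
|---|---|---|
| 1% | 1% | 1 − 0.99² = 2.0% |
| 2% | 2% | 1 − 0.98² = 4.0% |
| 5% | 5% | 1 − 0.95² = 9.8% |
| 10% | 10% | 1 − 0.90² = 19.0% |

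These are shares of two-term cases, not of all systemic allergic cases. A reaction with a third eligible component can survive the loss of one.

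**The case against.** The best defence is that Appendix 5 is a specific rule for a different question. The algorithm is meant to gain specificity by requiring symptoms close in time, and imputed dates cannot serve a window of one day either side. SAP 4.9.1 moves a partial start date to the first dose or to the first of the month, so pairs built on those dates would be artificial. That stands. It argues against feeding imputed dates into the window, and it means a reader should not infer that Appendix 5 directly breaks a rule: the conservative statements do not address concomitance. What remains is an unexplained departure from their principle.

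A reader might also infer that the reaction disappears from the report. It does not. Under SAP 4.9.1 each component stays in the tables by system organ class and preferred term, in the severity and duration tables, and in the by-subject listing with its relatedness. Events leading to epinephrine use are tabulated and listed as well. What is lost is recognition of the combination as a systemic allergic case.

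Partial onset dates should also be uncommon. Protocol 6.2.1.4 asks for date and time of onset, diaries are reviewed at visits (6.2.7), and data checks raise queries (9.2.1). Symptoms of one reaction are likely to be recorded together, which favours the lower end of the range. This too stands, although SAP 4.9.1 itself provides for missing days, months and whole dates.

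Finally, pairing on any overlap has a price. A missing day in a 30-day month widens the window from 3 days to 30 + 2 = 32. Common skin and airway terms could then pair by chance, and one related term would make the pair a related case. That is a good reason not to make overlap the main rule.

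**Conclusion.** The point holds as a cheap improvement to a safety definition. Appendix 5 handles incomplete dates in a way that departs, without explanation, from the principle stated in protocol 8.2.2.4 and SAP 4.8.1.2 and from the retention of such events in SAP 4.9.1. Its effect runs one way for subjects with any systemic allergic case and for subjects with a related case. It would be too strong to say that every reported count can only fall, because the unrelated row can rise by reclassification. Narrow-term and Category A cases are not affected.

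The size cannot be taken from the documents and is probably small. The range of 1–2% of two-term cases at q = 1% and 5–10% at q = 5% rests on an assumed q, on the same q for both components, and on gaps lying somewhere between fully correlated and independent. It should not be read as an estimate of missed reactions in this trial.

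**What to change.** Replace the last bullet of Appendix 5 with text to this effect:

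1. The rule concerns onset dates only. An event with a full onset date and a partial end date stays eligible for pairing.
2. The main count keeps the current one-day rule for events with full onset dates.
3. A pre-specified sensitivity count treats an event with a partial onset date as potentially concomitant when its possible range of dates overlaps the other event's date, plus or minus one day.
4. These candidates, and events with no onset date, go to the Blinded Data Review already planned in SAP 4.4. Confirmed cases enter the tables of events of special interest and are flagged in the listing.

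Record the change and its reason in SAP 4.13. The cost is a few lines of SAP text, minor programming and some review time. Some candidate pairs will be rejected, because a missing day widens the window to about a month; blinded review and the flag keep that visible.
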